8.1.4 Events of Special Interest

Events of special interest (ESIs) will be monitored over time, regardless of whether these events were reported as AEs. Any events that qualify as an AE or SAE will be reported accordingly (see Sections 8.1, 8.2, and 8.3).

ESIs will include hepatic abnormalities, muscle-related abnormalities, new-onset diabetes mellitus (NODM) and/or hyperglycemia, renal abnormalities, and ophthalmic events (i.e., macular degeneration), described as follows:

- AST or ALT >3 × ULN;
- Bilirubin >2 × ULN;
- CK >5 × ULN;
- NODM or worsening of glycemic control;

Note: NODM is defined by 1 or more of the following criteria, based upon information from AE, medication, and laboratory data:

- o AE indicating new type 1 or type 2 diabetes;
- o Initiation of anti-diabetes medication with confirmation of the diagnosis of diabetes;
- HbA1c \geq 6.5% (48 mmol/mol); and/or
- o Two consecutive values of fasting plasma glucose that are ≥ 126 mg/dL (7.0 mmol/L).

Note: Worsening of glycemic control will be defined as an HbA1c increase from Baseline >0.5% and/or a new concomitant medication or increase in current antidiabetic therapy in a participant with a Baseline HbA1c $\ge 6.5\%$.

- Both eGFR <30 mL/min/1.73 m² AND a >25% decrease in eGFR from Baseline, calculated using the Chronic Kidney Disease Epidemiology Collaboration equation; and
- Macular degeneration.

These ESIs will be monitored through review of the AE and laboratory databases.

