4.2 Exclusion Criteria

Participants who meet any of the following criteria will be excluded from participation in the study:

- 1. Body mass index \geq 35 kg/m² at the Screening Visit;
- 2. Current clinically active/acute episode of CV disease, including but not limited to:
 - o Major adverse CV event within 3 months prior to randomization, including:
 - Non-fatal myocardial infarction;
 - Non-fatal stroke:
 - Hospitalization for heart failure; or
 - Hospitalization for unstable angina.
 - o New York Heart Association Functional Classification Class III or IV heart failure.
- 3. Patients who meet the lipid management targets as specified in the 2017 Japan Atherosclerosis Society Guidelines for Prevention of Atherosclerotic Cardiovascular Diseases;
- 4. Have an existing diagnosis of homozygous familial hypercholesterolemia;
- 5. Have an existing diagnosis of CETP deficiency;
- 6. Glycosylated hemoglobin (HbA1c) ≥10% at the Screening Visit;
- 7. Uncontrolled hypertension, i.e., supine systolic blood pressure ≥160 mmHg and/or supine diastolic blood pressure ≥100 mmHg, taken as the average of triplicate measurements. One retest will be allowed, at which point if the retest result is no longer exclusionary, the participant may be randomized;
- 8. Active muscle disease or persistent creatine kinase (CK) concentration >3 × the upper limit of normal (ULN). One retest will be allowed after 1 week to verify the result, at which point if the retest result is no longer exclusionary, the participant may be randomized;
- 9. Estimated glomerular filtration rate (eGFR) <60 mL/min/1.73 m², calculated using the Chronic Kidney Disease Epidemiology Collaboration equation⁶;
- 10. Hepatic dysfunction as evidenced by any laboratory abnormality as follows: gamma-glutamyl transferase, alanine aminotransferase (ALT), or aspartate aminotransferase (AST) >2 × ULN, or total bilirubin >1.5 × ULN;
- 11. Anemia, defined as hemoglobin concentration <11 g/dL for men and hemoglobin concentration <9 g/dL for women;
- 12. History of malignancy within 5 years prior to screening, with the exception of non-melanoma skin cancers;
- 13. History of alcohol and/or drug abuse within 5 years prior to screening;
- 14. Treatment with a statin that is not either atorvastatin or rosuvastatin;
- 15. Treatment with other investigational products or devices within 30 days or 5 half-lives, whichever is longer, prior to screening;

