8 SAFETY ASSESSMENTS

8.1 Adverse Events

An AE is defined as any untoward medical occurrence in a clinical investigation participant administered a pharmaceutical product, which does not necessarily have a causal relationship with this treatment. An AE can therefore be any unfavorable and/or unintended sign (including an abnormal laboratory finding), symptom, or disease temporally associated with the use of an investigational medicinal product, whether or not related to the investigational medicinal product. Participants in this study who experience an AE or SAE with or without a causal relationship with the study drug will be followed until the AE or SAE resolves or stabilizes per the Investigator's judgment. All AEs, including observed or volunteered problems, complaints, or symptoms, are to be recorded on the appropriate eCRF.

AEs, which include clinical laboratory assessment variables, will be monitored and documented from the Screening Visit (Visit 1) until completion of Visit 6. Participants should be instructed to report any AE that they experience to the Investigator, whether or not they think the event is due to study drug. Beginning at the date of the Screening Visit (Visit 1), Investigators should make an assessment for AEs at each visit and record the event on the appropriate AE eCRF.

Wherever possible, a specific disease or syndrome rather than individual associated signs and symptoms should be identified by the Investigator and recorded on the eCRF. However, if an observed or reported sign or symptom is not considered a component of a specific disease or syndrome by the Investigator, it should be recorded as a separate AE on the eCRF. Additionally, the condition that led to a medical or surgical procedure (e.g., surgery, endoscopy, tooth extraction, or transfusion) should be recorded as an AE, not the procedure itself.

Any medical condition already present at the Screening Visit (Visit 1) should be recorded as part of the medical history and not reported as an AE unless the medical condition or signs or symptoms present at Baseline change in severity, frequency, or seriousness at any time during the study. In this case, it should be reported as an AE.

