8.7 Clinical Laboratory Evaluations

Blood for chemistry and hematology will be obtained as indicated in Appendix A and sent to a central laboratory for analysis. See Appendix B for a complete list of analytes. Blood samples for chemistry and hematology must be obtained under fasting conditions (i.e., after the participant has fasted for approximately 8 hours). For the purposes of this study, fasting will be defined as nothing by mouth except water and any essential medications. If a participant is not fasting, the Investigator should reschedule the visit as soon as possible. Estimated glomerular filtration rate will be calculated using the Chronic Kidney Disease Epidemiology Collaboration equation.⁶ At the Screening Visit only, the chemistry panel will include HbA1c.

A urine pregnancy test will be performed for women of childbearing potential at the Screening Visit (Visit 1) prior to their participation in the study and at the Safety Follow-Up Visit (Visit 6), and the Early Termination Visit, if appropriate.

An FSH test will be performed at the Screening Visit prior to participation in the study in women <55 years of age for whom it has been ≥1 year since their last menstrual period to confirm a postmenopausal state.

Blood samples for PK assessment will be collected as indicated in Appendix A. On Day 1 (Visit 2), a PK sample will be collected pre-dose. The subsequent post-dose PK samples should be collected once at approximately the same time at each visit.

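### The therapy criterion for worsening of glycemic control depends on Baseline HbA1c of at least 6.5%, not on diabetes status, so a therapy increase in diagnosed diabetes below 6.5% meets no glycemic ESI criterion on scheduled data

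*Protocol*

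**What the plan says.** Protocol 8.1.4 lists NODM or worsening of glycemic control as a single ESI item and defines each part in a note.

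- **Worsening.** "Worsening of glycemic control will be defined as an HbA1c increase from Baseline >0.5% and/or a new concomitant medication", or an "increase in current antidiabetic therapy in a participant with a Baseline HbA1c" of 6.5% or more.
- **NODM.** "NODM is defined by 1 or more of the following criteria, based upon information from AE, medication, and laboratory data". The four criteria are an AE of new diabetes; "Initiation of anti-diabetes medication with confirmation of the diagnosis of diabetes"; HbA1c of at least 6.5%; and "Two consecutive values of fasting plasma glucose that are ≥ 126 mg/dL (7.0 mmol/L". Apart from the word new in the AE criterion, none of them requires that the participant was free of diabetes beforehand.

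Three other provisions matter.

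- **Eligibility (protocol 4.2).** The only glycemic exclusion is "Glycosylated hemoglobin (HbA1c) ≥10% at the Screening Visit". Diabetes itself is not excluded.
- **HbA1c schedule (protocol 8.7, Appendix A footnote j, Appendix B).** "At the Screening Visit only, the chemistry panel will include HbA1c". Fasting glucose belongs to the chemistry panel drawn at every visit.
- **Analysis (protocol 9.2.2.1, SAP 3.7.6).** NODM cases are summarized by severity and relationship to study drug. Worsening of glycemic control is not mentioned in either section.

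**The concern.** A Baseline HbA1c cut-off is a poor stand-in for having diabetes, because successful treatment can bring the value below it. The group left out is people with a known diagnosis, on treatment, with a Screening value under 6.5%. For them the question is whether glycemic control deteriorates on study drug. The criterion best suited to detect that, an escalation of their therapy, is closed to them.

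ESI incidence is a listed safety endpoint (SAP 2.3.3) and supports the secondary objective on safety and tolerability. Protocol 8.1.4 also says that ESIs are monitored whether or not they were reported as AEs, so the ESI definition is meant to work independently of AE reporting. For this group it does not. Where a glucose criterion does apply, it places long-standing diabetes in a category meant for new disease.

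**Working it through.** The plan gives no figure on this point, so there is none to reproduce. The check applies the written rules to hypothetical participants, all with diagnosed diabetes on treatment. Baseline HbA1c values of 6.2% and 6.6% are illustrative assumptions.

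**Inputs**

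1. Worsening, HbA1c limb: rise from Baseline above 0.5% (protocol 8.1.4).
2. Worsening, therapy limb: new medication or increased therapy, with Baseline HbA1c of at least 6.5% (protocol 8.1.4).
3. NODM laboratory criteria: HbA1c of at least 6.5%, or two consecutive fasting glucose values of at least 126 mg/dL (protocol 8.1.4).
4. Baseline is the last value before first dose (SAP 3.1.3). For HbA1c on the planned schedule, that is the Screening value.
5. No HbA1c is scheduled after Baseline (protocol 8.7, Appendix A).

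**Results on scheduled data**

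| Baseline HbA1c | Therapy increased | Two consecutive glucose values ≥126 mg/dL | Worsening | NODM (laboratory) |
|---|---|---|---|---|
| 6.2% | yes | no | no | no |
| 6.6% | yes | no | yes | no |
| 6.2% | yes | yes | no | yes |
| 6.6% | yes | yes | yes | yes |
| 6.2% | no | yes | no | yes |
| 6.6% | no | yes | no | yes |

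Rows 1 and 2 show the gap: the same therapy increase is an ESI at 6.6% and nothing at 6.2%. In row 3 NODM is the only label available, although the diabetes is not new. Rows 5 and 6 show that glucose values alone meet NODM on both sides of 6.5%, so the cut-off matters only for therapy changes.

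**Does the result depend on how the sentence is read?** The 6.5% condition could cover the therapy limb only, both limbs, or only the increase in current therapy (leaving new medication unrestricted). On all three readings it covers an increase in existing therapy. With no scheduled post-Baseline HbA1c, the HbA1c limb cannot be met on any of them. The table therefore stands on all three. An added drug below 6.5% is different: on the third reading it would count as worsening.

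**If an unscheduled HbA1c is drawn**

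- 6.2% to 6.9%: the rise is 0.7, above 0.5. Worsening is met unless the 6.5% condition also covers the HbA1c limb. NODM is met in either case, because 6.9% is at least 6.5%.
- 6.2% to 6.4% with therapy increased: the rise is 0.2 and the value is below 6.5%. Nothing is met.

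**Size.** The documents give no diabetes prevalence and no HbA1c distribution. Purely as an illustration, assume that 20% to 40% of the 108 planned participants have diabetes and that 25% to 50% of those have Screening HbA1c below 6.5%:

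- low: 108 × 0.20 × 0.25 = 5.4
- high: 108 × 0.40 × 0.50 = 21.6

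That is about 5 to 22 people, or 5.4 / 4 = 1.4 to 21.6 / 4 = 5.4 per arm, to whom the gap would apply. It counts people, not events. Therapy increases among them would be fewer, and nothing in the documents allows an estimate of how many.

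**The case against.** The strongest reply is that little is actually lost. Protocol 8.1 keeps a pre-existing condition out of AE reporting only "unless the medical condition or signs or symptoms present at Baseline change in severity, frequency, or seriousness at any time during the study", so worsened diabetes is reportable. The same section makes a laboratory abnormality an AE when it requires intervention, which covers therapy increased because of rising glucose. Fasting glucose is summarized by arm and visit (SAP 3.7.2), concomitant medications are reviewed at every visit, and AEs of special interest are flagged in the CRF (SAP 3.7.1). All of this stands. A reader might infer that glycemic deterioration in these participants would go unseen; the documents do not support that.

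Three further inferences also go too far.

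- **That a planned worsening count, or a planned split between new-onset and worsening, would be wrong.** No such table is planned. The two share one ESI item, so mislabelling between them would not change a total for that item. It would still put known diabetes into the planned NODM summary.
- **That any deterioration changes label at 6.5%.** Two fasting glucose values of at least 126 mg/dL meet NODM on either side.
- **That adding a drug in known diabetes would be recorded as new-onset.** The NODM medication criterion pairs initiation with confirmation of the diagnosis, and protocol 8.1.4.3 speaks of newly diagnosed disease. An add-on drug in someone already diagnosed does not fit naturally.

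It can also be said that the NODM mislabelling comes from the missing diabetes-free condition in that definition. That is true of the label. But adding that condition alone would take these participants out of NODM and leave their therapy increases in neither category, so the therapy limb needs its own correction.

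**Conclusion.** The point holds as a gap in ESI capture and classification. On scheduled data, a participant with diagnosed diabetes and Screening HbA1c below 6.5% whose antidiabetic therapy is increased meets no glycemic ESI criterion, while the same increase at 6.5% or above qualifies. With two consecutive fasting glucose values of at least 126 mg/dL, that participant can only be labelled NODM.

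This rests on three facts in the protocol: the wording of the therapy limb, the absence of a diabetes exclusion below HbA1c 10%, and HbA1c at Screening only. It does not rest on the assumed shares, and the number affected remains unknown. Safety is analysed descriptively, so no test or efficacy estimate changes. The correction is worth making because the stated rule misclassifies and the data needed to correct it are already collected.

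**What to change.** The change concerns event classification only, not the management of participants.

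1. In protocol 8.1.4, replace the Baseline HbA1c condition in the therapy limb by diabetes at Baseline, defined as any of: diabetes in the medical history, antidiabetic medication in use at Baseline, or Screening HbA1c of at least 6.5%.
2. State that this condition covers both new medication and increased therapy, and does not restrict the HbA1c limb.
3. Derive the same flag in SAP 3.7.6, summarize worsening alongside NODM by arm, and limit NODM to participants without the flag. List the change in SAP Section 5.

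The cost is a change of wording and one derived flag. Medical history, medications and Screening HbA1c are already collected, and the SAP is to be finalized before database lock. The reported count of worsening events may be slightly higher.

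Two limits remain. The HbA1c limb still has no scheduled data. A flagged participant with two high fasting glucose values but no therapy change would no longer count as NODM, and would be visible through AE reporting and the fasting glucose summaries instead.

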8.1.4.1 Guidelines for management of elevated liver enzymes

Discontinuation of study drug should be considered if any of the following occurs and other causes of liver enzyme elevations, such as concomitant medication, have been considered and ruled out:

- ALT or AST $> 8 \times ULN$;
- ALT or AST >5 × ULN for more than 2 weeks:
- ALT or AST >3 × ULN and total bilirubin >2 × ULN or international normalized ratio >1.5; or
- ALT or AST >3 × ULN with the appearance of fatigue, nausea, vomiting, right upper quadrant pain or tenderness, fever, rash, and/or eosinophilia (>5%).

Participant management is at the discretion of the Investigator. It is recommended to examine for the presence of associated signs and symptoms, e.g., jaundice and hepatomegaly, and to perform additional diagnostic investigations, including abdominal ultrasound and a viral serology screen.

8.1.4.2 Guidelines for monitoring and management of creatine kinase

If at any time after randomization a participant experiences a CK elevation $>5 \times$ ULN, the participant will undergo a repeat confirmatory assessment as soon as it is reasonably possible, preferably within 3 to 7 days of the laboratory result becoming available.

A repeat CK assessment will include a query for related symptoms.

If the repeat CK assessment confirms an unexplained (i.e., not associated with recent trauma or physically strenuous activity) CK abnormality >5 × ULN and the participant is asymptomatic, he/she should receive further assessment and investigation into the cause, assessment of whether there is renal injury, and measurement of CK approximately weekly, or more frequently if clinically indicated, until resolution. If CK levels continue to rise, the study drug should be discontinued.

If the participant is symptomatic, the following should be completed:

- Interruption of study drug;
- Clarification of the nature, duration, and intensity of muscle symptoms;
- Review of possible predisposing factors, such as unaccustomed exercise, heavy alcohol intake, and viral illness (consider performing serology);
- Evaluation for additional diagnoses or other conditions which can cause myopathy, including muscle tenderness (by physical examination), weakness, rash, measurement of serum creatinine, and/or dipstick urinalysis with microscopy, if indicated;
- Measurement of clinical chemistries to assess the possibility of lactic acidosis; and
- Follow-up of symptoms and CK until the abnormality has resolved.

If, based on the above evaluation, an alternative explanation is suspected, consideration can be given to resuming study drug once CK returns to Baseline levels.

If no alternative explanation exists, consideration should be given to withdrawing the participant from study drug treatment.

If the repeat CK assessment confirms an unexplained (i.e., not associated with recent trauma or physically strenuous activity) $CK > 10 \times ULN$, the participant should be withdrawn and given no further doses of study drug, even in the absence of symptoms. The signs and symptoms and laboratory assessments as outlined above should also be evaluated. The participant should continue being followed in the study for safety.

8.1.4.3 Guidelines for monitoring and management of new-onset diabetes mellitus

Diabetes mellitus may be newly diagnosed during the study as described in Section 8.1.4. If a participant is newly diagnosed with diabetes mellitus during the course of the study, the Investigator will recommend referral for initial diabetes education and management by an appropriate healthcare provider (e.g., diabetologist, endocrinologist, or primary care provider). Interventions for management may include diet and lifestyle counseling, self-monitoring of blood glucose, oral glucose-lowering medications, injectable medications, or insulin as deemed necessary by the treating physician based on the level of hyperglycemia and relevant symptoms.

8.1.4.4 Guidelines for monitoring and management of significant changes in renal function

If at any time after randomization a participant experiences both an eGFR <30 mL/min/1.73 m² AND a >25% decrease in eGFR from Baseline, calculated using the Chronic Kidney Disease Epidemiology Collaboration equation, the participant will undergo a repeat confirmatory assessment as soon as is reasonably possible, preferably within 3 to 7 days of the laboratory result becoming available. The Investigator will ensure optimal hydration of the participant and consider and/or review any potential nephrotoxic or reversible causes of the notable eGFR decrease (e.g., non-steroidal anti-inflammatory drug use). Additionally, the Investigator may discuss the management of the case with the Medical Monitor.

8.1.4.5 Guidelines for management of macular degeneration

In cases of suspected macular degeneration, participants will be referred for an ophthalmological consultation.

8.2 Serious Adverse Events

An AE or adverse reaction is considered serious if, in the view of either the Investigator or Sponsor, it results in any of the following outcomes:

- Death;
- A life-threatening AE;

Note: An AE or adverse reaction is considered "life-threatening" if, in view of either the Investigator or Sponsor, its occurrence places the participant at immediate risk of death. It does not include an event that, had it occurred in a more severe form, might have caused death.

• Requires hospitalization or prolongation of existing hospitalizations;

Note: Any hospital admission with at least 1 overnight stay will be considered an inpatient hospitalization. An emergency room or urgent care visit without hospital admission will not be recorded as a SAE under this criterion, nor will hospitalization for a procedure scheduled or planned before signing of informed consent, or elective treatment of a pre-existing condition that did not worsen from Baseline. However, unexpected complications and/or prolongation of hospitalization that occur during elective surgery should be recorded as AEs and assessed

for seriousness. Admission to the hospital for social or situational reasons (i.e., no place to stay, live too far away to come for hospital visits, respite care) will not be considered inpatient hospitalizations.

- A persistent or significant disability/incapacity or substantial disruption of the ability to conduct normal life functions;
- A congenital anomaly/birth defect; or
- An important medical event.

Note: Important medical events that do not meet any of the above criteria may be considered an SAE when, based upon appropriate medical judgment, they may jeopardize the participant and may require medical or surgical intervention to prevent 1 of the outcomes listed above. Examples of such medical events include allergic bronchospasm requiring intensive treatment in an emergency room or at home, blood dyscrasias or convulsions that do not result in inpatient hospitalizations, or the development of drug dependency.

8.3 Serious Adverse Event Reporting – Procedures for Investigators

Initial reports

All SAEs occurring from the Screening Visit (Visit 1) until completion of Visit 6 must be reported to within 24 hours of the knowledge of the occurrence. After completion of Visit 6, any SAE that the Investigator considers related to study drug must be reported to the or the Sponsor/designee.

To report the SAE, complete the SAE form electronically in the electronic data capture (EDC) system for the study. When the form is completed, personnel will be notified electronically by the EDC system and will retrieve the form. If the event meets serious criteria and it is not possible to access the EDC system, send an email to at [contact] or call the reporting line (phone number listed below), and fax/email the completed paper SAE form to (contact information listed in Section 8.6) within 24 hours of awareness. When the EDC system becomes available, the SAE information must be entered within 24 hours of the system becoming available.

Follow-up reports

[figure not shown]
The Investigator must continue to follow the participant until the SAE has subsided or until the condition becomes chronic in nature, stabilizes (in the case of persistent impairment), or the participant dies.

Within 24 hours of receipt of follow-up information, the Investigator must update the SAE form electronically in the EDC system for the study and submit any supporting documentation (e.g., participant discharge summary or autopsy reports) to via fax or email. If it is not possible to access the EDC system, refer to the procedures outlined above for initial reporting of SAEs.

